#### 5.3 Study Product Supply and Accountability 5.3.1 Product supply

The tenofovir douches will be compounded at the study site pharmacy (JHU). The Pharmacy Procedures Manual will specify the detailed compounding instructions. A designated Pharmacist of Record (PoR) will be available at the study site. At JHU, the PoR will also be the compounding pharmacist in the designated compounding areas. The enemas may be prepared in advance within the established guidelines based on available stability data. The API will be provided by CONRAD and sent directly to the site PoR or the compounding pharmacist.

Where possible, all raw materials will be provided from the same manufactured lot. The raw materials will be provided in bulk and will require measurement at each enema preparation. The raw materials (Table 7) that will be provided to each site for preparation of research unit enemas include:

Material	Raw Material Appearance
Tenofovir	White powder
Sodium chloride, NF	Pellets

#### Table 7. Study drug supply raw materials

Sodium hydroxide, 18% (w/v)	White granular powder
0.1N HCl	Colorless clear solution
0.1N NaOH	Colorless clear solution

### 5.3.2 Product accountability

All study products will be available to the study staff through the designated site pharmacy or compounding pharmacy, once they have been labeled appropriately by the PoR. The PoR is required to maintain complete records of all study products received and dispensed.

### **5.4 Study Product Dispensing**

Study products will be dispensed from the pharmacy to the designated study staff for an enrolled participant only upon receipt of a written prescription from an authorized prescriber as noted on the FDA 1572 form. Pre-procedural cleansing enemas will be administered by study participants. Study product enemas will be administered to subjects by study staff, in order to ensure maximal retention of study product in the desired anatomic compartment, and maximum comparability.

### 5.5 Adherence to Administration Guidelines

Research unit doses of study product will be administered either by the study site investigator or a designated co-investigator, with time of administration recorded in the study chart and on the CRF. Anything of note during this process will be recorded in the source documents.

#### **5.6 Concomitant Medications and Procedures**

With the exception of medications listed as prohibited, enrolled study participants may use concomitant medications during study participation. All concomitant medications, over-the-counter preparations, vitamins and nutritional supplements, and herbal preparations reported throughout the course of the study will be recorded in the source documents and on case report forms designated for that purpose.

#### **5.7 Prohibited Medications and Procedures**

Participants will be advised to refrain from RAI or any practices which include rectal insertion of any product, including those used during sexual intercourse (drug/medication, penis, other objects, sex toy, or enema) for 72 hours before and after the research unit study product dose and 7 days after each flexible sigmoidoscopy with biopsy collection.

Study participants will be prohibited from using the following medications throughout the study period: heparin (including Lovenox®), warfarin, Plavix® (clopidogrel bisulfate), immunomodulary medications, rectally administered products containing N-9 (including over-the-counter products), or investigational products. Other drugs, such as aspirin or NSAIDS that are associated with increased likelihood of bleeding following mucosal biopsy, should be restricted for use prior to flexible sigmoidoscopy as required by clinical guidelines.

Based on the tenofovir U.S. prescribing information, concomitant use of tenofovir with medications that decrease renal function or compete for active tubular secretion may increase concentrations of tenofovir or other renally eliminated medications. Therefore, oral PrEP in the prior 21 days (based on self-report) will not be allowed.

If participants report using any of these medications or products while on study or within the specified time frame noted, their study participation will be put on hold, pending discussions with study site investigator, DREAM Program Chair who is the IND Sponsor, and/or the study medical officer. Study staff will actively review medication use with each research participant during screening and throughout study participation. Participants will also be queried as to their adherence regarding insertion of rectal products 72 hours before and after study product exposure and 7 days after each biopsy collection visit.

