## 4.1 Inclusion Criteria

- Between the ages of 15-24 at Screening
- Cisgender male who has sex with other men
- Willing and able to communicate in English
- Willing and able to provide informed consent to take part in the study
- Participant demonstrates capacity to comprehend, evaluate, reason, and express a choice about their participation in study
- For youth ages 15-17, have parent or caregiver consent to take part in the study
- Willing and able to provide adequate locator information
- Express initial interest in participating in a douching study
- Understand and agree to local HIV/STI reporting requirements
- HIV-1 uninfected at screening as documented by HIV-1 antigen/antibody 4th generation testing
- Willingness and availability to attend all study visits, barring unforeseen circumstances
- Per participant report at screening, consensual RAI in prior 6 months
- Live in or around the Baltimore area.
- Willing to abstain from insertion of anything (drug/medication, digits, penis, object, sex toy, or douche) into the anorectum for 72 hours before and after each study visit and 7 days after the biopsy collection.
- Willing to refrain from aspirin, vitamins and herbal supplements, and NSAID use for one week before and after each study biopsy visit
- Agrees not to participate in other research studies involving drugs and/ or medical devices for the study's duration

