Rectal Specimens: Biopsies for PK/PD (Not conducted in participants < age 18; Prioritized for participants age 18 and above)	• Perform flexible sigmoidoscopy with biopsy collection at 24 ± 2 hrs post-dose per each participant's designated specimen collection schedule (moderate sedation may be used for pediatric participants less than 18 years)	• Perform flexible sigmoidoscopy with biopsy collection at 72 ± 4 hrs post-dose per each participant's designated specimen collection schedule (moderate sedation may be used for pediatric participants less than 18 years)
Rectal Specimens: Rectal Fluid for PK measurement (Not conducted in participants < age 18; Prioritized for participants age 18 and above) and microbiomeassessment* (collected in all participants)	
 
Collect rectal fluid at 24 ± 2 hr
 
Collect rectal swab for microbiome assessment*
 
	• Collect rectal fluid at 72 ± 4 hr post-dose per each participant's designated specimen collection schedule

Table 11: Visit 4 (Day 2) and Visit 5 (Day 4)– Sampling Visit

\* Microbiome and rectal fluid collection will be collected prior to dosing or enema administration and microbiome collection should precede rectal fluid collection.

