## 6.7 Visit 6- Termination Visit- 96 hour (Day 5 + 3 days)

The Termination Visit ideally should occur at 96 hours (+3 day window) for all participants. The term visit should be at least 24 hours after the last scheduled biopsy. This visit will serve as the participant's study termination.

During their Termination Visit, participants will complete an exit in-depth interview (IDI) that will explore their experiences participating in the study, user-centered suggestions for product design and delivery, factors influencing product use in the future, and suggestions to maximize YMSM's engagement in future biomedical trials, including how to overcome perceived barriers and challenges based on their experiences. The IDI will be conducted using video-conferencing by a trained interviewer located at the University of Pennsylvania.

If a participant withdraws from study participation early or is withdrawn early from study participation by the study team, they will be asked to come in for an Early Termination Visit and the all the activities conducted at the Termination Visit will also be conducted for the Early Termination Visit.

Component	Procedure/Analysis	
Administrative	
 
Review/update demographic and locator information
 
Review STI risk reduction counseling and provide condoms
 
	
Clinical	
 
Review/update medical history
 
Review/update concomitant medications
 
Review any available test results
 
Complete AE assessment
 
Symptom-directed physical exam as needed
 
Obtain vital signs (HR, BP, Temp)
 
Collect blood specimens for:
 
	
Safety Labs and STI Screening: blood	
 
Collect blood specimens for:         
 
CBC with differential
 
CMP
 
HIV-1 antigen/antibody 4th generation testing (confirmatory tests as needed) *
 
Syphilis Testing (confirmatory test as needed) *
 

 
 
 
	
Safety Labs and STI Screening: urine and rectal	
 
Collect urine sample for GC/CT (NAAT) *
 
Collect rectal swab for GC/CT (NAAT) *
 
Collect swab for HSV, if indicated *
 
	
Other Specimens (rectal fluid, etc.)	• Collect specimens as appropriate/indicated (if the participant is willing) *	
Behavioral	Completion of exit in-depth interview	

Activities to take place at the Termination Visit include: **Table 12: Termination Visit** 

\*If indicated and/or per local standard of care.

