## 6.8 Exit Follow-up Phone Call

After the final study visit, follow-up call or early termination visit, a final contact may be required to provide laboratory test results (e.g. GC/CT) and post-test counseling. Anyone testing positive for HIV or an STI will be linked to appropriate care. All contacts will be documented in participant study records.

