## **Rectal Exam, Cleansing Enema, and Rectal Specimen Collection:**

The participant will be positioned in the left lateral decubitus position for the following procedures:

- Rectal exam: The examiner will conduct a visual examination of the anus and surrounding area and note any abnormality. The examiner will then insert a lubricated (Good Clean Love, Good Clean Love, Inc. Eugene, OR) gloved finger into the anal canal and sweep around the internal anal circumference.
- Rectal specimen collection: Swabs for GC/CT will be inserted into the rectum and placed in contact with the rectal wall, turned 360 degrees and then removed.
- Rectal fluid will be collected by using a swab/sponge inserted through the anoscope to come into contact with the rectal wall for 2 minutes to absorb rectal fluid.

- A pre-procedural cleansing enema will be self-administered prior to flexible sigmoidoscopy for baseline and 72 hour post-dosing assessment.
- Rectal biopsies collection via flexible sigmoidoscopy: Up to 20 biopsies will be taken via a flexible sigmoidoscope at approximately 10-20 cm from the anal verge using large-cup biopsy forceps. The number of biopsies to be collected will vary depending on individual subject schedule and study site. Biopsies will be performed at different times in order to limit the number of total biopsies for each participant, but still achieve a rich post-dose sampling picture overall given the 6 different biopsy sampling times across all participants.

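### No adverse event, medication or rectal-insertion review is scheduled after Visit 6, which in the 72 h biopsy group can come 24 h after up to 20 biopsies, inside the protocol's own one-week post-biopsy precautions

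*Combined protocol and SAP*

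**What the plan says.** Four parts of the combined protocol and SAP bear on the week after the post-dose biopsy.

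- **Drug limit.** Section 4.1 makes this an entry condition: "Willing to refrain from aspirin, vitamins and herbal supplements, and NSAID use for one week before and after each study biopsy visit". Section 5.7 covers aspirin and NSAIDs during the study, saying that they "should be restricted for use prior to flexible sigmoidoscopy as required by clinical guidelines"; it gives no period and does not name supplements. Section 5.6 is permissive: "With the exception of medications listed as prohibited, enrolled study participants may use concomitant medications during study participation".
- **Rectal insertion.** Section 5.7 asks participants to avoid rectal insertion and says they will be queried about "insertion of rectal products 72 hours before and after study product exposure and 7 days after each biopsy collection visit".
- **Biopsy.** Section 6.13 states: "Up to 20 biopsies will be taken via a flexible sigmoidoscope". The latest schedule, in Section 6.6, has "biopsy collection at 72 ± 4 hrs post-dose".
- **End of observation.** Section 6.7 places Visit 6 at 96 h with a 3-day allowance, treats it as study termination, and adds: "The term visit should be at least 24 hours after the last scheduled biopsy". Section 6.8 says that "a final contact may be required to provide laboratory test results (e.g. GC/CT) and post-test counseling". Appendix I marks adverse event assessment and medication review up to Visit 6. Its phone-call column, labelled as needed only, is marked for review of laboratory results alone.

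**The concern.** The protocol sets two precautions lasting a week after biopsy and then ends scheduled observation before that week is over. Section 5.7 promises medication review throughout participation, but participation stops at Visit 6. No scheduled contact remains at which the 7-day insertion query can be completed for the post-dose biopsy. The week after the baseline biopsy is not at issue, because Visit 3 must fall more than 7 days after Visit 2.

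Adverse events of Grade 2 or higher are the primary safety endpoint (Section 2.2), and Section 7.5.1 asks participants to report events only until they complete participation. After the reporting period, only serious events learned of passively are reported (Section 7.4, EAE Reporting Period). A new, non-serious Grade 2 event, such as bleeding on the second or third day after a 72 h biopsy, could therefore fall after the last review. Any aspirin, NSAID or supplement use, or rectal insertion, in those days would also go unrecorded.

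**Working it through.** **Inputs.** Post-dose biopsies are at 1, 6, 24 or 72 h, with tolerances of 40 min, 40 min, 2 h and 4 h (Tables 10 and 11). Four participants are planned per time point (Section 6.5). Visit 6 is at 96 h plus up to 3 days (Section 6.7), read here as 96 to 96 + 72 = 168 h. The precaution lasts 7 days = 168 h (Sections 4.1 and 5.7). Healing takes 3 days = 72 h (Section 12.3.1).

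**The plan's own figure.** For the 72 h group at the earliest Visit 6, 96 − 72 = 24 h, which matches the 24 h minimum in Section 6.7.

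**Time reviewed and time left, nominal biopsy times.** Week end = biopsy + 168 h. Reviewed = Visit 6 − biopsy. Left = week end − Visit 6.

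| Biopsy | Week ends | Reviewed, Visit 6 at 96 h | Reviewed, Visit 6 at 168 h | Week left after Visit 6 |
|---|---|---|---|---|
| 1 h | 169 h | 95 h | 167 h | 73 to 1 h |
| 6 h | 174 h | 90 h | 162 h | 78 to 6 h |
| 24 h | 192 h | 72 h | 144 h | 96 to 24 h |
| 72 h | 240 h | 24 h | 96 h | 144 to 72 h |

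In the 72 h group, 144 to 72 h is 6 to 3 days of the 7. With the 4 h tolerance, that group's week ends at 236 to 244 h.

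**Against the three-day healing time.** At the earliest Visit 6 the 1 h and 6 h groups have passed 72 h and the 24 h group has just reached it (70 to 74 h with its tolerance). The 72 h group has 24/72 = one third. Its healing period ends at 72 + 72 = 144 h, so it falls short whenever Visit 6 comes before 144 h. That is (144 − 96)/(168 − 96) = 48/72 = 67% of the allowed window's length. This is a share of the window, not a probability, since the documents do not say when visits will actually occur.

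**Scale of risk.** Section 12.3.1 gives a rate only for perforation, 1 in 1,000 to 1 in 10,000 procedures. The chance of at least one in 4 procedures is 1 − (1 − p)^4, which is 0.04% at p = 0.0001 and 0.4% at p = 0.001. No rate is given for bleeding, so the expected number of missed Grade 2 events cannot be computed.

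**What one event would do.** Section 9.6 plans exact 95% intervals. For 0/16 the upper limit is 1 − 0.025^(1/16) = 20.6%. For 1/16 the upper limit solves (1 − p)^16 + 16p(1 − p)^15 = 0.025, giving 30.2%; the lower limit is 1 − 0.975^(1/16) = 0.2%. A single missed event would be visible in the summary, if one occurred.

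**Timing of a later call.** With dosing on Day 1, Day 12 is 11 × 24 = 264 h, which is 20 h after the latest week end (244 h). Day 14 is 13 × 24 = 312 h. Added participation runs from 264 − 168 = 96 h (4 days) to 312 − 96 = 216 h (9 days). Dosing is at most 45 days after screening, so the call is at most 45 + 13 = 58 days after it.

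**The case against.** The safety objective concerns the douche. Counted from the single dose, every schedule has the same adverse event window, and a late biopsy complication in at most four people says little about the product. The last PK and PD samples are at 72 ± 4 h, so nothing a participant does after Visit 6 can change them. Both arguments stand, and they limit the point to procedure-related safety.

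There are also safeguards. Reported events are followed until they resolve or stabilize (Section 7.5.1). Interim visits are possible at any time during the study (Section 6.9). Expedited reporting runs to the final study contact, which need not be Visit 6. Visit reminders are scheduled through Visit 6. The Data Safety and Management Plan, the procedures manual or the consent forms, none of which is in the supplied text, may restate the drug limit or add follow-up. A site could also use the optional call for the insertion query. These reduce the concern but do not remove it: in the supplied text no review is scheduled after Visit 6, and the call is optional and marked for laboratory results. The 24 h minimum in Section 6.7 suggests a deliberate choice of interval, but it does not fit the 7-day query in Section 5.7.

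A reader might infer that Visit 6 precedes the end of the post-biopsy week on every schedule. In the 1 h group that rests on 168 h against 168.3 h (1 h less 40 min, plus 168 h). It fails if the 3 days are calendar days: with dosing at 09:00 on Day 1, a Day 8 visit at 15:00 is at 7 × 24 + 6 = 174 h, past the 1 h group's week end and level with the 6 h group's. The 72 h group is unaffected by this choice.

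A reader might also infer that Sections 4.1 and 5.7 contradict each other. They do not: 5.7 is silent on the time after biopsy, so the fault is an incomplete cross-reference.

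**Conclusion.** The point holds as a gap in follow-up after the procedure. The protocol orders a 7-day insertion query and asks for a one-week drug limit, but it schedules nothing after Visit 6 to review either, or to capture new adverse events. The gap matters mainly for the 72 h group, which is at most 4 of 16 participants. It could be fewer, since under-18s are not biopsied and sampling in others may be limited to blood (Section 3). In that group Visit 6 may come 24 h after up to 20 biopsies, with about 3 to 6 days of the week unobserved at nominal times.

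The possible loss is late, non-serious, procedure-related events of Grade 2 or higher. The number may be zero, and Section 12.3.1 calls bleeding, infection and perforation extremely rare. The documents do not support a claim that the safety assessment of the douche is biased, or that any PK, explant, histology or microbiome result is affected. The conclusion assumes that the unseen plans and manuals add no later contact. It calls for a cheap improvement, not a redesign.

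**What to change.** 1. Make the Section 6.8 call mandatory for every biopsied participant, or for all dosed participants (including those under 18) if a common adverse event window is wanted. Hold it after the post-biopsy week has ended, for example on Day 12-14.
2. Include participants terminated early under Section 7.11 who remain willing. They are endpoint cases, and Section 13.3 stops data collection after permanent discontinuation, so the text must say that this call is still allowed for them.
3. At the call, review adverse events, concomitant medications and rectal insertion. Mark these in Appendix I, and define the call as the final study contact for adverse event reporting.
4. Tabulate events arising after Visit 6 separately, so that the window up to Visit 6 can still be read on its own.
5. As a minor wording point, repeat the Section 4.1 one-week before-and-after drug window in Section 5.7. State that it adds no new hold on participation, because 5.7 already has a hold rule and listing supplements there could otherwise delay dosing.

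The cost is protocol wording, the Appendix I entries and about 16 short calls, more if participants are replaced. Participation lengthens by about 4 to 9 days, depending on when Visit 6 occurs. The call falls at most 58 days after screening, within the 2-3 months stated in Section 3.4.

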#### **5.8 Recommended Procedures**

Condoms are recommended for use by all participants enrolled in this study. The study site will provide male condoms to participants in quantities expected to be sufficient for the study period. These condoms will not be coated with any type of spermicide. Using condoms provided by the study will be recommended for all sexual encounters during the study period. In the event that a participant needs additional supply of condoms between visits, he may request these from study sites at any time. If, after completing the study, the study participant wishes to receive prescribed oral HIV PrEP, the study team will assist with making a referral to an appropriate clinical provider.

[figure not shown]
# 6. STUDY PROCEDURES

### 6.1 Study overview

This section includes information on visit-specific study procedures. An overview of the study visits and evaluations is available in protocol Appendix I: Schedule of Events. Unless otherwise specified, the laboratory procedures listed in this section are performed at the local study site laboratories.

As needed per institutional policy, participants may be required to undergo COVID-19 symptom screening prior to all visits. If a participant screening is positive, the participant will be tested for COVID-19. Additionally, participants may be required to undergo pre-procedure COVID-19 testing within 72hrs of any biopsy visit. If the screening or pre-procedure results indicate COVID infection, the study visit (including the procedure visit) will be canceled. If negative, the participant will be allowed to move forward. Positives will be able to move forward once cleared.

#### Figure 3. ATN Dream Study Visit Schedule

## 6.2 Recruitment: Pre-Screening

We will recruit YMSM who have expressed interest in being contacted to screen for eligibility into a Phase I HIV prevention biomedical trial. As part of participant outreach and recruitment strategies, study staff can pre-screen potential study participants at either on-site or off-site locations. During these interactions, study staff may explain the study to potential participants and ascertain elements of presumptive eligibility (e.g., willingness to use the study products, willingness to adhere to the study requirements, etc.), to be confirmed at an on-site screening visit. Process information (e.g., number of potential participants contacted, number presumptively eligible) may be recorded and stored at the study site. Procedures and documentation will comply with local IRB requirements. Participants will be asked to share their contact information and preferred mode of communication so that study team members can schedule an in-person Screening visit at Johns Hopkins University. Eligible YMSM will be contacted by site staff to schedule an in-person visit at the ATN site. To be accommodating to the needs of young participants, multiple visits may be scheduled to complete all required screening procedures, if necessary.

